2. STUDY OBJECTIVES

2.1 Primary objective

The primary objective of this study is to determine change from baseline of LH area under the concentration curve from time zero to 8 hours postdose [$AUC_{(0-8)}$] at Day 7 in comparison to placebo.

2.2 Secondary objectives

The secondary objectives of the study are:

- To determine the change from baseline of free and total testosterone on Days 7 and 28

- To assess the safety and tolerability of multiple dosing of AZD4901 in patients with PCOS
- To measure AZD4901 and AZ12592232 plasma exposure in patients with PCOS
- To evaluate the PK/pharmacodynamic (PD) relationship of AZD4901 and LH and testosterone

2.3 Exploratory objectives

The exploratory objectives of this study are:

- To monitor changes from baseline of LH (Day 28 only); follicle-stimulating hormone (FSH), estradiol (E2), progesterone, prolactin, thyroid-stimulating hormone (TSH), T4 (total and free), and insulin-like growth factor-1 (IGF-1; as surrogate for growth hormone to avoid diurnal variation) on Days 7 and 28; and glycosolated haemoglobin (HbA_{1c}) on Day 28
- To explore the impact of AZD4901 on health-related quality of life (HRQoL) as measured by change from baseline at Day 28
- To explore the impact of AZD4901 on PCOS-specific patient-reported outcomes symptoms as measured by change from baseline at Days 7, 14, 21, and 28

Results of the above exploratory analyses, if available, will be reported in the Clinical Study Report (CSR).

- To collect and store deoxyribonucleic acid (DNA) for future exploratory research into genes that may influence response, ie, distribution, safety, tolerability, and efficacy of AZD4901 treatment

The results of the pharmacogenetic analysis, if performed, will be reported separately from the CSR.

3. STUDY PLAN AND PROCEDURES

3.1 Overall study design and flow chart

This is a randomised, double-blind, double-dummy, placebo-controlled, parallel-design study of a multiple dosing of placebo or AZD4901 to investigate effects of AZD4901 on the GnRH axis. Women with PCOS between the ages of 18 and 45 years, inclusive, are eligible for study participation. Patients will be randomly assigned to 1 of the following 4 treatments: 20 mg AZD4901 once daily, 20 mg AZD4901 twice daily, 40 mg AZD4901 twice daily, or placebo. There will be 56 patients enrolled (14 patients per cohort) to have approximately 12 evaluable patients in each of the 4 cohorts. The investigational product (IP) will be administered orally beginning on Day 1 and continuing through the morning of Day 28. To

maintain study blinding, AZD4901 and/or matching placebo will be administered such that 2 tablets are taken twice daily for all treatment groups (see Section 5.5.2).

Study screening will begin up to 60 days prior to the baseline visit to allow a washout period for patients taking oral contraceptives. Patients who discontinue oral contraceptives and patients who do not require washout from oral contraceptives, but who have screening assessments more than 3 weeks prior to the baseline visit, will return to the clinic on Days -21 to -2 for repeat laboratory assessments. Patients not taking oral contraceptives who have screening assessments within 3 weeks of the baseline visit do not need to repeat laboratory tests.

[figure not shown]
Following the screening period, the study duration from baseline through the follow-up visit will be approximately 6 weeks for each patient. Eligible patients will report to the clinic on Day -1 for baseline assessments and will receive supplies of IP to begin dosing on Day 1 as an outpatient. A diary card will be provided to record the date and time of each dose. Patients will be given symptoms diary paper questionnaires for home assessments. On Days 7, 14, 21, and 28, patients will return to the clinic to take their morning dose of IP and to complete scheduled assessments. If it is not practical for patients to return to the clinic prior to the morning dose on Days 14 and 21, patients may take the morning dose of IP at home and report to the clinic later in the day for study assessments. A follow-up visit will occur at approximately Day 42.

On Days -1, 7, and 28, multiple samples for the analyses of LH, FSH, and testosterone profiles will be collected prior to dosing until 8 hours following the morning dose. On Day -1, sampling will begin just prior to the anticipated time of dosing on subsequent study days and continue for 8 hours. Intensive sampling should begin by 9 AM on Day -1 and will be initiated at approximately the same time on each subsequent visit (± 1 hour). Patients will be asked to complete the HRQoL short form 36 (SF-36; see [Appendix E](#)) at baseline (Day -1) and on Day 28. A site symptoms questionnaire will be completed at each study visit from Day -1 through Day 28 (see [Appendix F](#)). A symptoms diary questionnaire will be completed at the patients' homes each evening from Day -1 through Day 28. Serial PK samples will be collected prior to dosing until 8 hours following the morning dose on Days 7 and 28. On Days 14 and 21, patients will report to the clinic to undergo safety assessments.

Safety evaluations will include assessment of AEs, use of concomitant medications, clinical laboratory tests, measurement of vital signs, 12-lead electrocardiograms (ECGs), physical examinations, and Columbia-Suicide Severity Rating Scale (C-SSRS) assessments.

A study flow chart is presented in [Figure 1](#), a schedule of all assessments is presented in [Table 1](#), and the details of blood sample collection are presented in [Table 2](#).

Figure 1 Study flow chart

Outpatient administration of IP begins the morning of Day 1 for all treatments. A window of ± 1 day is allowed for the Day 7, 14, 21, and 28 visits.

^a There will be 56 patients (14 per each treatment group) enrolled to have approximately 12 evaluable patients in each treatment group.

^b Applies only to patients who require washout of oral contraceptives or have a screening visit more than 3 weeks prior to the baseline visit.

Table 1 Study plan

	Screening ^a		Baseline					Follow-up	Early discontinuation
	Visit number	1	2	3	4	5	6	7	8
	Study day relative to first dose	-60 to -2	-21 to -2	-1	+7±1	+14±1	+21±1	+28±1	+42±3
Informed consent	X								
Review of inclusion/exclusion criteria	X	X							
Demography	X								
Medical/surgical history	X								
Ultrasound	X ^b								
Serology assessment ^c	X								
Test for alcohol and drugs of abuse ^d	X		X						
Pregnancy test	X ^e	X	X	X	X	X	X	X	X
Randomisation			X						
Dispense IP ^f			X						
Dispense dosing diary ^g			X						
Fast for 2 hours prior to and 1 hour following morning dose				X			X		
Administer morning dose in clinic				X	X ^h	X ^h	X ⁱ		
Assessment of compliance				X	X	X	X		
Return of unused IP ^f				X	X	X	X		
Record concomitant medications ^j	X	X	X	X	X	X	X	X	X
Record AEs ^k	X	X	X	X	X	X	X	X	X
Physical examination ^l	X		X				X	X	X

Table 1 Study plan

	Screening ^a		Baseline					Follow-up	Early discontinuation
	Visit number	1	2	3	4	5	6	7	8
	Study day relative to first dose	-60 to -2	-21 to -2	-1	+7±1	+14±1	+21±1	+28±1	+42±3
Weight	X		X	X			X	X	X
Height and BMI	X								
Vital signs ^m	X		X	X			X	X	X
12-lead ECG	X		X	X ⁿ			X ⁿ	X	X
Haematology ^o	X	X	X	X	X	X	X	X	X
Clinical chemistry	X	X	X	X	X	X	X	X	X
Urinalysis	X	X					X	X	X
C-SSRS ^p			X	X	X	X	X	X	X
Pharmacokinetic samples ^q				X			X		X
HRQoL - SF-36			X				X		X
Symptoms site questionnaire			X	X	X	X	X		X
Symptoms diary questionnaire ^r			X	X	X	X	X		
High frequency LH samples ^s			X	X			X		
Well-defined FSH ^t			X	X			X		
Single sample LH	X	X						X	X
Single sample FSH	X							X	X
Single sample testosterone (total/free)	X	X						X	X
Well-defined testosterone (total/free) ^t			X	X			X		
4-β-OH cholesterol			X				X ^u		

Table 1 Study plan

	Screening ^a		Baseline					Follow-up	Early discontinuation
Visit number	1	2	3	4	5	6	7	8	
Study day relative to first dose	-60 to -2	-21 to -2	-1	+7±1	+14±1	+21±1	+28±1	+42±3	
6-β-OH testosterone			X				X ^u		
TSH and T4 (total and free) ^v	X		X	X			X	X	
HbA _{1c} ^v			X				X	X	
IGF-1, progesterone, E2 ^v			X	X			X	X	
Prolactin ^v	X		X	X			X	X	
Consent and blood sample for genetic analysis (optional) ^w				X					

BMI body mass index; HIV human immunodeficiency virus; OH hydroxy; SAE serious AE.

^a Patients who must discontinue the use of oral contraceptives prior to the study will return to the clinic on Days -21 to -2 for repeat laboratory assessments. Patients who do not require a washout of oral contraceptives, but screening assessments were performed more than 3 weeks from the baseline visit, will also return to the clinic on Days -21 to -2 for repeat laboratory assessments.

^b May be performed if there is no previously-documented ultrasound for diagnosis of PCOS.

^c Screen for HIV, hepatitis B, and hepatitis C.

^d Random drug and alcohol screening at subsequent visits may be performed at the discretion of the Investigator. See Section 6.3.5 for a list of analytes.

^e Serum pregnancy tests will be performed at screening only; urine tests will be performed at all other time points.

^f The first dose of IP is to be taken the morning of Day 1 as an outpatient. On Day -1, patients will be given sufficient IP for at-home dosing for the duration of the study. At each clinic visit, the patient should return all unused supplies of IP.

^g The patient will be asked to record the dosing dates and times for all IP administration and bring the diary to each clinic visit for review. On Days 6 and 27, ie, the days prior to the serial PK and PD assessments, the sites should contact the patients by telephone to ensure the morning and evening doses were recorded and to remind patients to hold the morning dose on Days 7 and 28 until clinic arrival.

^h On Days 14 and 21, it is suggested patients take their morning dose of IP in the clinic; however, if this is not practical, dosing may occur at home with the patient reporting to the clinic later in the day for scheduled procedures.

ⁱ On Day 28, only a morning dose is taken.

^j All concomitant medications taken from 12 weeks prior to dosing are to be recorded.

^k All SAEs will be recorded from the time informed consent is signed; nonserious AEs will be recorded beginning at the baseline (Day -1) visit.

^l Full physical examinations will be performed at screening and follow-up/early discontinuation; brief examinations will be performed on Days -1 and 28. See Section 6.3.6 for details of the assessments.

- ^m Blood pressure and pulse rate will be measured after patient has rested in a supine position for 10 minutes.
- ⁿ Electrocardiograms will be recorded at 2 hours postdose on Days 7 and 28.
- ^o Including hematocrit at screening and at the follow-up (or early termination) visit.
- ^p A patient reporting suicidal ideation of Type 4 or 5 or suicidal behaviour as measured by the C-SSRS during the study will be discontinued and referred for appropriate assessment and treatment.
- ^q On Days 7 and 28, PK samples will be collected prior to the morning dose, and at 20 minutes, 40 minutes, and 1, 1.5, 2, 3, 4, 6, and 8 hours postdose. A single sample will be collected in the event of early discontinuation.
- ^r The symptoms diary questionnaire should be completed at home each evening before patients go to bed.
- ^s Luteinizing hormone samples will be collected prior to the morning dose (on Days 7 and 28; on Day -1, the 0 h sample will be collected prior to the anticipated time of dosing on subsequent study days) and every 10 minutes following dosing through 8 hours postdose. Intensive sampling should begin by 9 AM and will be initiated at approximately the same time at each visit (± 1 hour). The first sample will be collected within 30 minutes prior to dosing or at an approximately matched time at the baseline visit.
- ^t Testosterone (total and free) and FSH will be collected prior to dosing (on Days 7 and 28; on Day -1, the 0 h sample will be collected prior to the anticipated time of dosing on subsequent study days) and hourly for 8 hours postdose; the first sample will be collected within 30 minutes prior to dosing or at an approximately matched time at the baseline visit.
- ^u The 4- β -OH cholesterol and 6- β -OH testosterone samples will be collected prior to dosing on Day 28.
- ^v Component of the monitoring sample (includes estradiol [E2], progesterone, prolactin, TSH, T4 [total and free], HbA_{1c}, and IGF-1) and will be collected ± 1 hour of the same time each scheduled day beginning on Day -1 and for all subsequent visits. Thyroid tests (TSH and total/free T4) and prolactin only will be performed at screening to assess study eligibility. The HbA_{1c} will not be performed on Day 7.
- ^w If informed consent is given for the optional genetic sampling, a single sample may be collected on Day 7 (Visit 3) or at any time after randomisation and stored for future analysis.

Table 2 Blood sample collection schedule

Study day	Scheduled time	Safety laboratory ^a	PK	LH	FSH	Testosterone (total/free)	4-β-OH cholesterol/ 6-β-OH testosterone	Monitoring sample ^b	Genetic
Screening		X		X ^c	X ^c	X ^c		X ^d	
Rescreening ^e		X		X ^c		X ^c			
Day -1	0 h	X		X	X	X	X	X	
	0-8 hours ^f			Every 10 min	Hourly	Hourly			
Day 7	0 h (predose)	X	X	X	X	X		X ^g	X ^h
	0-8 hours ⁱ		Serial ^j	Every 10 min	Hourly	Hourly			
Day 14		X							
Day 21		X							
Day 28	0 h (predose)	X	X	X	X	X	X	X	
	0-8 hours ⁱ		Serial ^j	Every 10 min	Hourly	Hourly			

Table 2 Blood sample collection schedule

Study day	Scheduled time	Safety laboratory ^a	PK	LH	FSH	Testosterone (total/free)	4-β-OH cholesterol/ 6-β-OH testosterone	Monitoring sample ^b	Genetic
Follow-up		X		X ^c	X ^c	X ^c		X	
Early termination		X	X ^c	X ^c	X ^c	X ^c		X	

^a Haematology and clinical chemistry at all time points with serology and serum pregnancy assessments at screening only and hematocrit at screening and follow-up.

^b Monitoring sample includes estradiol (E2), progesterone, prolactin, TSH, T4 (total and free), HbA_{1c}, and IGF-1.

^c Single sample only.

^d Only TSH, total/free T4, and prolactin assessed at screening to determine study eligibility.

^e Applies only to patients who require washout of oral contraceptives or have a screening visit more than 2 weeks prior to the baseline visit.

^f On Day -1, LH samples will be collected prior to the anticipated time of the morning dose on subsequent study days and every 10 minutes through 8 hours; FSH and testosterone (total and free) will be collected prior to the anticipated time of the morning dose on subsequent study days and every hour through 8 hours.

^g HbA_{1c} will not be collected on Day 7.

^h If informed consent is given for the optional genetic sampling, a single sample may be collected on Day 7 (Visit 3) or at any time after randomisation and stored for future analysis.

ⁱ On Days 7 and 28, LH samples will be collected prior to the morning dose and every 10 minutes through 8 hours postdose; FSH and testosterone (total and free) will be collected prior to the morning dose and every hour through 8 hours postdose.

^j On Days 7 and 28, PK samples will be collected prior to the morning dose, and at 20 minutes, 40 minutes, and at 1, 1.5, 2, 3, 4, 6, and 8 hours postdose.

3.2 Rationale for study design, doses and control groups

The current study design includes an oral administration of AZD4901 tablets to fully explore the PD, safety, and PK of AZD4901 with an 8-hour intensive collection of blood samples at a predose baseline then on Days 7 and 28 following the daily dose. As GnRH levels cannot be measured in this study, it is anticipated that any modulation of GnRH release in patients receiving AZD4901 will result in a change from baseline in LH AUC₍₀₋₈₎ hours and this is the primary endpoint of the study.

Day 7 has been selected as the primary endpoint for LH measurement as AZD4901 will be at steady state and also to avoid any impact should a patient have downstream hormonal effects from the modulation of their HPG axis. Day 28 has been selected to assess the longer term efficacy on testosterone and the duration of the effects on LH secretion.

In vitro AZD4901 completely blocked agonist (senktide)-induced calcium flux in CHO cells stably expressing human NK-3 receptors with a concentration of drug causing an IC₅₀ of 2.57 nM.

[figure not shown]
In vivo AZD4901 dose-dependently reversed senktide-induced suppression of locomotor activity in the gerbil by both the intraperitoneal and oral routes. In this study, the brain:plasma ratio for AZD4901 was approximately 0.2. However, there is evidence that the NK-3 receptors relevant to the current development are to be exposed to the systemic circulation ([Norsted et al 2008](#)).

In the clinical trials to date, suppression of testosterone was seen at all doses, with the effect persisting for 24 hours at the highest monotherapy dose of 80 mg once daily or with 15 mg twice daily or 30 mg twice daily. It appears that AZD4901 modulates the HPG axis but does not suppress it completely.

Based on population PK-PD modelling and simulation, the observed PK differences (higher C_{max}, similar AUC) in the fed compared to the fasted state, will not lead to significant differences in testosterone change. It was also concluded that following a 40 mg twice-daily treatment, trough AZD4901 concentration will be higher compared to 80 mg once daily. The time above IC₅₀ for testosterone inhibition after 40 mg twice daily of AZD4901 is 80.9% time of the dosing interval compared to only 55.7 % after 80 mg once daily. The mean predicted peak testosterone concentrations at steady state are lower and overall less variable during 24 hours for a 40 mg twice-daily dose compared to an 80 mg once-daily dose. These findings suggest twice-daily dosing provides a sustained testosterone suppression effect during the dose interval.

Modelling data are presented in [Figure 2](#).

Figure 2 Serum testosterone concentration over 24 hours at AZD4901 steady state

Note: the curves are modelled from the existing clinical dataset. BID twice daily; QD once daily.

4- β -hydroxy cholesterol is being measured in the study to give an early indication of whether AZD4901 has the potential to induce *CYP3A4*. 6- β -hydroxy testosterone is being measured to support the conclusion that any reduction in testosterone levels have been caused by AZD4901 action at the NK3R rather than changes in *CYP3A4* metabolism.

Based on previous clinical observations in PK and PD responses, expected bioavailability, safety profiles, toxicity investigation in preclinical species, and on the assumption that receptor occupancy needs to be maintained for continuous suppression of testosterone, the doses of 20 mg once daily, 20 mg twice daily, and 40 mg twice daily have been selected to allow characterisation of the dose response curve.

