AZD4901 20-mg tablets and matching placebo will be administered orally. On Days 7 and 28, patients will take their morning doses of investigational product in the clinic with 240 mL of water. On Days 14 and 21, patients may report to the clinic for their morning dose, if practical. Otherwise, all doses will be taken as an outpatient with a sufficient amount of water.

Duration of treatment

Following a screening period of 60 days maximum, the study duration from baseline through the follow-up visit will be approximately 6 weeks for each patient. Apart from required in-clinic dosing on the mornings of Days 7 and 28 and optional in-clinic dosing the mornings

of Days 14 and 21, investigational product will be taken on an outpatient basis twice daily from Day 1 through the morning dose on Day 28. A follow-up visit will occur at approximately Day 42.

Outcome variable(s):

- Pharmacokinetics: Where possible, the following pharmacokinetic parameters will be determined for AZD4901 and AZ12592232 for Day 7 and Day 28:
 - C_{max} : Maximum observed plasma concentration.
 - t_{max} : Time of C_{max} .
 - $AUC_{(0-8)}$: Area under the plasma concentration-time curve from time zero to 8 hours
 - C_{min} : Predose concentration
 - C_{max} metabolite to parent ratio: The ratio of AZ12592232 C_{max} to AZD4901 C_{max}
 - $AUC_{(0-8)}$ metabolite to parent ratio: The ratio of AZ12592232 $AUC_{(0-8)}$ to AZD4901 $AUC_{(0-8)}$

The following will be calculated for 4- β -hydroxy cholesterol and 6- β -hydroxy testosterone:

- Ratio of post treatment (Day 28) to pretreatment (Day -1) concentration
- Pharmacodynamics:
 - Primary: $AUC_{(0-8)}$ for LH on Day 7
 - Secondary: Change-from-baseline (Day-1) for free and total testosterone concentrations on Days 7 and 28; and $AUC_{(0-8)}$ for LH on Day 28

Where possible, the following secondary pharmacodynamic parameters will be determined for LH, testosterone, and FSH samples collected on Days -1, 7, and 28: free and total testosterone $AUC_{(0-8)}$, FSH $AUC_{(0-8)}$, an evaluation of LH pulse interval and amplitude, free and total testosterone C_{max} , free and total testosterone C_{min} , FSH C_{max} , FSH C_{min} , and $AUC_{(0-8)}$ for LH.

- Exploratory: Change-from-baseline (Day-1) for LH (Day 28 only), FSH, and the components of the monitoring sample (estradiol [E2], progesterone, prolactin, thyroid-stimulating hormone, T4 [total and free], and insulin-like growth factor- 1) on Day 7 and Day 28

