1.4 Benefit/risk and ethical assessment

In clinical trials to date, AZD4901 has been well tolerated and dose escalations have been driven by the effects on testosterone levels that are now a key marker for efficacy in this new development. Nonclinical data indicate a potential for hepatotoxicity, but this has not been observed in the clinical program to date and patient's liver function will be monitored during their participation in the current trial.

AZD4901 may have the potential to induce and also inhibit *CYP3A4/5* enzymes. Due to the potential CYP induction/inhibition risk, concomitant use of AZD4901 with narrow therapeutic index drugs that are metabolised by *CYP3A4/5* should be avoided. Investigators should be aware that the exposure of other drugs metabolised by *CYP3A4* could be altered. See [Table 3](#) for a list of restricted medications.

As a disease of younger females, the patients in the trial are necessarily of childbearing potential, although PCOS often impairs fertility. Patients will be required to use reliable contraception throughout the trial. Hormonal contraception is disallowed as it could impact the primary efficacy measurements.

Polycystic ovary syndrome can result in disruption of menstruation, infertility, virilisation, and, in the longer term, serious metabolic consequences. Treatments are available, but are intended to suppress symptoms of PCOS with variable effectiveness. AZD4901 represents a possibility to effect the underlying biology of PCOS and this study is the first step to validate that hypothesis. As such, the benefit:risk is positive and administration of AZD4901 to women with PCOS is justified.

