11.3 Calculation or derivation of pharmacokinetic variables

The PK analyses will be the responsibility of pharmacokineticist at . standard operating procedures (SOPs) and Work Instructions will be used as the default methodology, if not otherwise specified. The actual sampling times will be used in the PK calculations.

Pharmacokinetic parameters will be derived using standard noncompartmental methods with WinNonlin[®] Professional Version 5.2, or higher (Pharsight Corp., Mountain View, California, United States). All PK computations will be performed using WinNonlin[®] Professional Version 5.2 (or higher), or SAS[®] Version 9.2 or higher (SAS Institute, Inc., Cary, North Carolina, United States).

Patients who withdraw from the study following administration of the IP, but prior to study completion, will be included in the PK analysis provided they have evaluable concentrations over the planned collection period. Patients with partial data will be evaluated on a case-by-case basis to determine if sufficient data are available for meaningful analysis.

Where possible, the following PK parameters will be determined for AZD4901 and AZ12592232 for Day 7 and Day 28:

- C_{\max} : Maximum observed plasma concentration.
- t_{\max} : time of C_{\max} .
- $AUC_{(0-8)}$: Area under the plasma concentration-time curve from time zero to 8 hours calculated by linear up/log down trapezoidal summation.
- C_{\min} : predose concentration
- C_{\max} metabolite to parent ratio: The ratio of AZ12592232 C_{\max} to AZD4901 C_{\max}
- $AUC_{(0-8)}$ metabolite to parent ratio: The ratio of AZ12592232 $AUC_{(0-8)}$ to AZD4901 $AUC_{(0-8)}$

The following will be calculated for 4- β -OH cholesterol and 6- β -OH testosterone:

- Ratio of post treatment:pre treatment concentration

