12.1.3 Pharmacokinetic analysis set

The PK analysis set will be a subset of the safety analysis set and will include only patients who receive at least 1 dose of AZD4901 and have at least 1 postdose PK measurement without important CSP deviations or violations thought to significantly affect the PK (eg, patient vomited at or before 2 times median t_{\max} , wrong dose administered, prohibited concomitant medication, etc).

For the evaluation of the 4- β -OH cholesterol and 6- β -OH testosterone results, this population will be further restricted to include only patients who did not receive any inhibitors/inducers within 12 weeks prior to dosing.

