12.2.5 Pharmacokinetics

The PK blood sample collection times, as well as derived sampling time deviations, and plasma concentrations will be listed for all patients. Plasma concentrations will be summarised by treatment using descriptive statistics (eg, n, arithmetic mean, SD, minimum, median, maximum, geometric mean, and CV).

Plasma concentrations that are below the lower limit of quantitation (LLOQ) will be handled as follows:

- At a time point where less than or equal to 50% of the values are below the limit of quantitation (BLQ), all BLQ values will be set to LLOQ, and all descriptive statistics will be calculated.
- At a time point where more than half of the values are BLQ, the mean, SD, geometric mean and CV will be set to Not Determined. The maximum value will

be reported from the individual data, and the minimum and median will be set to BLQ.

- If all values are BLQ at a time point, no descriptive statistics will be calculated for that time point. Not applicable will be reported for SD and CV and BLQ will be reported for mean, geometric mean, minimum, median, and maximum.
- The number of BLQ values (n below LLOQ) will be reported for each time point.

Plasma parameters will be summarised by treatment using descriptive statistics (eg, n, arithmetic mean, SD, minimum, median, maximum, geometric mean, and CV). For t_{\max} , only n, median, minimum, and maximum will be reported.

Data from patients excluded from the PK analysis set will be included in the data listings, but not in the summaries.

Concentration and PK parameters [$AUC_{(0-8)}$, C_{\min} , and C_{\max}] for AZD4901 and AZ12592232 will be presented graphically for Day 7 and Day 28 for each treatment.

Results for 4- β -OH cholesterol and 6- β -OH testosterone will be summarised by treatment and collection time. For 4- β -OH cholesterol and 6- β -OH testosterone, descriptive statistics will include the ratio of post treatment to pre treatment concentration with 90% confidence intervals (CIs) calculated by ln-transformed data.

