12.3 Determination of sample size

The sample size for this study was selected to be consistent with the research hypothesis as described in Section 1.2.

The proposed sample size is 12 evaluable patients per dose cohort with a total of 56 patients for the entire study (2 dropouts per group assumed). This study provides 76 % power versus placebo to detect a 30% change from baseline in LH at Day 7 and testosterone for the cohort at Day 28 (see Table 6).

Table 6 Sample size power

Assumed LH and testosterone change from baseline at Day 28	Evaluable subjects required		
	70% power	80% power	90% power
30% change	11	14	18
40% change	7	8	11

The number of patients that will agree to participate in the genetic research is unknown. It is therefore not possible to establish whether sufficient data will be collected to allow a formal statistical evaluation or whether only descriptive statistics will be generated. A statistical analysis plan will be prepared where appropriate.

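### The planned raw Day 28/Day -1 ratio of 6-β-hydroxy testosterone mixes CYP3A4 activity with the expected fall in testosterone, so it can hide an induction contribution when both mechanisms act

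*Protocol*

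**What the plan says.** Section 3.2 gives the purpose of the 6-β-hydroxy testosterone assay: it "is being measured to support the conclusion that any reduction in testosterone levels have been caused by AZD4901 action at the NK3R". The alternative to be argued against is altered CYP3A4 metabolism. The same paragraph introduces 4-β-hydroxy cholesterol separately, as a first signal of CYP3A4 induction.

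The analysis variable appears in three places, with the same content:

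- Synopsis, outcome variables: "Ratio of post treatment (Day 28) to pretreatment (Day -1) concentration".
- Section 11.3: "Ratio of post treatment:pre treatment concentration".
- Section 12.2.5: "descriptive statistics will include the ratio of post treatment to pre treatment concentration with 90% confidence intervals (CIs) calculated by ln-transformed data".

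None of these relates the metabolite to testosterone. Section 11.3 does define metabolite-to-parent ratios, but only for AZ12592232 over AZD4901.

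Four other passages matter:

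- Section 1.4: "AZD4901 may have the potential to induce and also inhibit" CYP3A4/5, so neither direction of enzyme change can be assumed away.
- Section 12.3: the study is sized with "power versus placebo to detect a 30% change from baseline in LH at Day 7 and testosterone", so movement in the substrate is expected.
- Section 12.1.3: the PK analysis set "will include only patients who receive at least 1 dose of AZD4901". The evaluation of this marker uses a further restriction of that set and so contains no placebo patients.
- Table 2: 6-β-hydroxy testosterone and total testosterone are both drawn at 0 h on Day -1 and Day 28.

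**The concern.** Section 3.2 treats 6-β-hydroxy testosterone as a readout of CYP3A4 metabolism of testosterone. The concentration of such a metabolite depends on enzyme activity and on how much substrate there is. AZD4901 is expected to lower the substrate through NK3R, and it may also change the enzyme. The raw post/pre ratio is the product of the two effects.

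The case that matters is a testosterone fall produced partly by NK3R action and partly by CYP3A4 induction. The two effects push the raw ratio in opposite directions. A flat or reduced ratio could then be read as showing no induction, and the whole fall credited to NK3R action. What is at stake is the mechanistic interpretation of the testosterone result, not the estimate of the testosterone change or the primary LH comparison.

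**Working it through.** The plan states no figure for this marker, so there is none to reproduce. The check is a steady-state mass balance, with every quantity relative to baseline.

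**Inputs**

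- p: testosterone production factor (NK3R action).
- k: CYP3A4 activity factor. It may be above or below 1 (section 1.4).
- f: share of testosterone clearance that runs through CYP3A4. The protocol does not give it, so it is an assumption shown over 0.1 to 1.0.
- Scenario: testosterone falls to 0.70, reading the 30% change in section 12.3 as a fall.
- Elimination of the metabolite is held constant.

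**Formulas**

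- Testosterone: T = p / ((1 − f) + f·k)
- Raw metabolite ratio (the planned variable): M = k·T
- Metabolite over testosterone: M/T = k

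**Case 1: NK3R action only.** With p = 0.70 and k = 1, T = 0.70 and M = 1 × 0.70 = 0.70 for any f. M/T = 1.00. The raw ratio falls 30% although CYP3A4 has not changed.

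**Case 2: induction only, testosterone to 0.70.** With p = 1, solving for k gives k = (1/0.70 − (1 − f))/f, and M = 0.70·k.

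| f | k needed (= M/T) | raw M |
|---|---|---|
| 1.0 | 1.43 | 1.00 |
| 0.8 | 1.54 | 1.08 |
| 0.5 | 1.86 | 1.30 |
| 0.3 | 2.43 | 1.70 |
| 0.1 | 5.29 | 3.70 |

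**Case 3: both mechanisms.** With p = 0.7 and k = 1.5:

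| f | T = 0.7/((1 − f) + 1.5f) | raw M = 1.5·T | M/T |
|---|---|---|---|
| 0.1 | 0.7/1.05 = 0.667 | 1.00 | 1.50 |
| 0.3 | 0.7/1.15 = 0.609 | 0.91 | 1.50 |
| 0.5 | 0.7/1.25 = 0.560 | 0.84 | 1.50 |
| 0.8 | 0.7/1.40 = 0.500 | 0.75 | 1.50 |

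CYP3A4 activity is up by half in every row, yet the raw ratio is flat or reduced.

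**Case 4: one raw ratio, several explanations.** Because M = k·T, a raw ratio of 0.70 arises from k = 0.7 with T = 1.00, k = 1.0 with T = 0.70, k = 1.5 with T = 0.47, or k = 2.0 with T = 0.35. The raw ratio alone cannot tell these apart. Dividing by T can.

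**The case against.** The strongest objection is that the raw ratio does discriminate for the question asked. Section 3.2 concerns a reduction in testosterone. Faster metabolism could cause that; inhibition would raise testosterone. If one mechanism acts alone, the raw ratio is 0.70 under NK3R action and 1.00 or more under induction. This stands, and it rules out three stronger readings that a reader might infer:

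- That the raw ratio cannot separate NK3R action from CYP3A4 change at all. It separates single mechanisms by direction; it fails for mixtures.
- That it would show no change when induction caused the entire fall. That needs f = 1. For every smaller f, pure induction raises the raw ratio, and nothing in the protocol supports f = 1.
- That a ratio of 0.70 would lead to the fall being blamed on inhibition. It may look like reduced CYP3A4 activity, but with testosterone down inhibition is not a rival cause.

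Second, the denominator is already planned. Sections 11.4 and 12.2.6 give time-matched ln-ratios to baseline for total testosterone, so dividing one geometric mean ratio by the other yields the normalised point estimate. This stands in part. The protocol plans no such step and no confidence interval for the quotient, and the two summaries rest on different analysis sets (12.1.3 and 12.1.4).

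Third, 4-β-hydroxy cholesterol gives separate evidence on induction. It does mitigate, but section 3.2 gives the attribution of a testosterone fall to the other marker.

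Fourth, the wording of 12.2.5 is not exclusive, and a SAP could add the normalised ratio. That is possible. The protocol nevertheless names one derived variable in three places, and it suits its stated purpose poorly.

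Finally, no objective in sections 2.1 to 2.3 names this marker, and no test, power statement or decision rule uses it. This stands and limits the severity.

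**Conclusion.** The concern holds in a limited form. Read alone, the planned raw ratio confounds substrate supply with CYP3A4 activity and can conceal an induction contribution when NK3R action and induction occur together. In the worked example, a 50% rise in activity appears as a raw ratio between 1.00 and 0.75 for f from 0.1 to 0.8.

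The result assumes that metabolite concentration is proportional to testosterone times CYP3A4 activity and that metabolite elimination is unchanged. The size of the distortion depends on f, which is not documented; the confounding itself does not.

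A related weakness is that 12.1.3 confines the evaluation to AZD4901 recipients, so the ratio has no concurrent reference for drift over time or in the assay.

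Severity is minor to moderate. The marker is supportive, and the primary LH comparison and the testosterone comparisons do not depend on it.

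**What to change.** 1. In the synopsis and in sections 11.3 and 12.2.5, make the main variable for this marker the within-patient change ln(6-β-hydroxy testosterone / total testosterone) at Day 28 minus the same quantity at Day -1. Use the 0 h samples, and back-transform to a ratio with a 90% CI.
2. Keep the raw Day 28/Day -1 ratio as a descriptive summary.
3. To allow a comparison with placebo, amend 12.1.3 so that placebo patients are included in the evaluation of this marker. Changing 11.3 and 12.2.5 alone would not permit that comparison.

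Cost: a change of wording and a small additional analysis. No new blood is needed, because Table 2 already schedules both analytes at 0 h on both days. The one possible extra expense is assaying the placebo samples for the metabolite. Section 6.5.3 does not say whether this is planned, and the for-cause rule for placebo samples in 6.5.2 is written for drug concentrations.
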